	11.4 INVESTIGATOR SITE FILE	
	11.3 CLINICAL TRIAL SUPPLIES	
	11.2 REQUIRED DOCUMENTS PRIOR TO STUDY INITIATION	. 47
	11.1 PARTICIPATING CENTERS	. 47
11.	STUDY ADMINISTRATION	. 47
	10.4 Data Management	. 46
	10.3 QUALITY LABORATORY STANDARDS	. 46

GLOSSARY

Abbreviation/Term Definition

5-ASA 5-aminosalicylic acid 6-MP 6-mercaptopurine AE Adverse event

ALT Alanine aminotransferase
ASI Application Setup Instructions
AST Aspartate aminotransferase

ATC Anatomical Therapeutic Chemical (Classification)

C_{avg} Average bertilimumab serum concentration

CDM Clinical Data Management
CDMoP Clinical Data Monitoring Plan
CFR Code of Federal Regulations

CI Confidence interval

 C_{max} Maximum serum concentration C_{min} Minimum serum concentration

CRF Case report form (also eCRF for electronic CRF)

CRO Contract research organization

CV% Coefficient of variance

DEHP Di (2-ethyl hexyl) phthalate also known as Di-octyl phthalate (DOP)

DM Data Management

EDC Electronic Data Capture ECP Eosinophil cationic protein

ECG Electrocardiogram

ELISA Enzyme-linked immunosorbent assay

EMA European Medicines Agency FDA Food and Drug Administration

GCP Good Clinical Practice

HIV Human immunodeficiency virus

Hr Hour

hs-CRP High sensitivity C-reactive protein

ICF Informed consent form

ICH International Conference on Harmonisation

IEC Independent Ethics Committee

IgG Immunoglobulin G

IRB Institutional Review Board

IV Intravenous kg Kilogram

LOCB Last observation carried backward LOCF Last observation carried forward

MedDRA® Medical Dictionary for Regulatory Activities

mg Milligram

MI Multiple imputation
mITT Modified intent to treat

mL Milliliter

Abbreviation/Term Definition

mM Millimolar

MOH Ministry of Health

NSAID Non-steroidal anti-inflammatory

PBS Phosphate buffered saline

PD Pharmacodynamic

PGA Physician's Global Assessment

PI Principal Investigator
PK Pharmacokinetic
PP Per protocol

PPD Purified protein derivative

PVC Polyvinyl chloride
SAE Serious adverse event
SAP Statistical analysis plan
SD Standard deviation

SOP Standard operating procedures

SUSAR Suspected unexpected serious adverse reaction

TB Tuberculosis

T_{1/2} Half-live of bertilimumab in serum
TEAE Treatment emergent adverse event

T_{max} Time to reach maximum bertilimumab serum concentration

TNF Tumor necrosis factor
TPN Total parenteral nutrition

UC Ulcerative colitis

UCEIS Ulcerative Colitis Endoscopic Index of Severity

ULN Upper limit of normal
WHO World Health Organization
WMA World Medical Association

1. INTRODUCTION

1.1 ULCERATIVE COLITIS

Ulcerative colitis (UC) is a chronic and relapsing inflammatory disease characterized by diffuse mucosal inflammation limited to the colon and rectum without evidence of any specific causative pathogens [1]. The disease course is characterized by exacerbations (including symptoms of diarrhea, abdominal pain, and rectal bleeding) and remissions [2, 3]. The worldwide incidence rates of UC range between 1.25 to 20.3 new cases per 100,000/year, with approximately 10–12 new cases per 100,000/year in North America and Europe [4-7].

The goal of the medical treatment in UC is to rapidly induce a steroid-free remission while at the same time preventing complications of the disease itself and its treatment. The choice of treatment depends on severity, localization and the course of the disease. More extensive or severe disease is treated with oral and local 5-ASA compounds and corticosteroids to induce remission. Patients who do not respond to this treatment require hospitalization, intravenous (IV) steroids or, when refractory, calcineurin inhibitors (cyclosporine, tacrolimus), tumor necrosis factor-α antibodies (infliximab, adalimumab) or immunomodulators (6-mercaptopurine [6-MP], azathioprine) [3, 8-10].

1.1.1 The Role of Eotaxin and Eosinophils in Inflammatory Bowel Disease

Eotaxin-1 is an eosinophil-selective chemokine that is constitutively expressed in the intestine and various other tissues [11]. It is produced by a variety of cell types including eosinophils, epithelial cells, fibroblasts, endothelial cells, T-lymphocytes, monocytes and macrophages following induction by pro-inflammatory mediators [12]. Eotaxin is known to play a significant role in the tissue accumulation of eosinophils that accompanies allergic inflammation. While eosinophils are an important component of innate immunity, the accumulation of eosinophils in tissues can be detrimental. Eosinophil degranulation products have significant cytotoxic effects on tissues, and cytokines known to be released by eosinophils enhance inflammatory signaling.

An association between eosinophils and the initiation of mucosal injury and clinical relapse in UC [13, 14] and Crohn's disease [15] has been documented, and serum eotaxin levels are increased in patients with these diseases [16, 17]. These studies provide strong rationale for the use of therapeutic agents targeting eosinophils and molecules that regulate eosinophil function such as eotaxin-1 in the treatment of UC.

1.2 INVESTIGATIONAL THERAPY

Bertilimumab is a human monoclonal immunoglobulin G (IgG) 4 antibody that neutralizes human eotaxin-1 and inhibits its function. The product is manufactured in a mammalian cell line engineered using recombinant DNA technology to produce the antibody.

1.2.1 Nonclinical Studies

A single-dose toxicity study with bertilimumab was conducted in Rhesus monkeys (6 per dose group). Monkeys were administered a single IV infusion of bertilimumab at a dose of 10 or 100 mg/kg and observed for 28 and 7 days, respectively. No effects on morbidity or mortality were observed. Body weights and food consumption were not impacted by bertilimumab treatment and all clinical chemistry and hematological parameters examined were unaffected. In a repeat-dose toxicity study, Rhesus monkeys (6 per dose group) were administered 10, 30 or 100 mg/kg bertilimumab twice weekly by IV infusion for 28 days. There were no deaths or significant morbidity following treatment with bertilimumab. No effects on clinical chemistry, ophthalmoscopic or hematological parameters or body weight

were observed. At sacrifice (end of study period), there were no treatment-related changes in organ weight or macroscopic/microscopic observations. For detailed information on preclinical studies, please refer to the Investigator's Brochure.

1.2.2 Clinical Studies

Three clinical studies of bertilimumab were conducted in Europe: a Phase 1 study in healthy volunteers (study CAT-213-0101), and Phase 2 studies in patients with allergic rhinitis and allergic conjunctivitis (studies CAT-213-0103 and CAT-213-0203, respectively). Ninetynine (99) individuals have received bertilimumab: 45 via the intravenous (45/99, 45%), eight (8) via the intranasal (8/99, 8%), and 46 via the topical ocular (46/99, 46%) route of administration. Thirteen individuals received IV bertilimumab at doses ≥500 mg (maximum dose administered: 770 mg). In these studies, bertilimumab was well tolerated and no doserelated adverse events (AEs) were noted. To date, no clinical studies of bertilimumab have been conducted in patients with UC. For additional information on these clinical studies, please refer to the Investigator's Brochure.

1.3 STUDY RATIONALE

Bertilimumab is the first monoclonal antibody to specifically neutralize human eotaxin-1. Bertilimumab has been shown to interrupt the eotaxin-stimulated migration of cells and may therefore be useful in the treatment of human diseases such as UC, where eosinophil accumulation is an important feature.

The purpose of this study is to evaluate the safety and efficacy of bertilimumab compared to placebo in adult patients with active moderate to severe UC. The treatment period will include three IV infusions of bertilimumab (10 mg/kg) or placebo at two-week intervals, on study Days 0, 14 (± 2 days) and 28 (± 2 days). Subjects will be followed for an additional 9 weeks after the end of treatment on study Days 35, 42, 56 and 90 (± 3 days per follow-up visit). The study design will allow evaluation of the safety and efficacy of bertilimumab over the treatment and follow-up periods using validated assessment tools. In addition, the pharmacokinetics (PK) and pharmacodynamics (PD) of bertilimumab will be assessed throughout the study.

1.3.1 Rationale for Dose Selection

Immune Pharmaceuticals has chosen to evaluate an IV dose of 10 mg/kg bertilimumab every 2 weeks based on the following safety, PK and PD data:

- No safety concerns were identified in Study CAT-213-0101, in which subjects received a single IV bertilimumab dose of up to 10 mg/kg (corresponding to absolute doses of 570 to 770 mg in four subjects), or in Study CAT-213-0103, in which subjects received a single IV bertilimumab dose of up to 500 mg.
- The PD endpoint in Study CAT-213-0101, eotaxin-induced eosinophil shape change, was inhibited by serum from all subjects who received bertilimumab doses of 1 mg/kg and higher, with nearly 100% inhibition in the 5 mg/kg and 10 mg/kg dose groups. A shape change in eosinophils is considered a requisite process in chemotaxis, and can be taken as evidence of an impending migratory response. Maximum inhibition occurred at concentrations of ~40 μg/mL. At 35 days post-dose, high levels of inhibition were still observed despite low concentrations of bertilimumab, suggesting that the PD response was prolonged when compared with the bertilimumab plasma concentrations.
- In Study CAT-213-001, after a single dose of 5 mg/kg, unbound bertilimumab had a mean half-life of 211 hours (CV% 30.5); the mean half-life after a single 10 mg/kg

dose was 194 hours (CV% 27.1). The half-life of total bertilimumab (bound plus unbound) is estimated to be 16-20 days. The data from this study also suggest dose proportionality in bertilimumab exposure between these two doses.

• No antibodies to bertilimumab were detected in any of the three previous single-dose clinical trials.

Systemic markers of bertilimumab activity (peripheral blood eosinophil count, serum levels of eotaxin-1, ECP, and hs-CRP), as well as eosinophil count and eotaxin level in intestinal tissue, and their correlation with the therapeutic response in UC patients will be also assessed.

1.3.2 Allergic and Infusion Reactions

Monoclonal antibodies, including fully human antibodies, can cause allergic or non-allergic infusion reactions when administered intravenously, and three subjects in bertilimumab clinical trials have experienced infusion reactions, one serious. Accordingly, several precautions have been instituted in the protocol to decrease the risk of infusion reactions and possible anaphylaxis, including the administration of study drug^f in a controlled setting with ready availability of antihistamines, fluids, epinephrine, and staff trained in the management of anaphylaxis and a pre-study drug regimen with antihistamines, acetaminophen and corticosteroids.

Grading of infusion reactions will be made according to the criteria set forth in Appendix D, as are criteria for anaphylaxis, by definition, a grade 4 reaction. Management of-study drug infusion in the event of an infusion reaction is set forth in Appendix D as well; if additional interventions beyond interruption of-study drug infusion are indicated, then the investigator should manage the reaction according to his or her clinical judgement and any applicable institutional protocols.

2. STUDY OBJECTIVES AND ENDPOINTS

2.1 STUDY OBJECTIVES

Primary Objective

• To evaluate, in patients with active moderate to severe UC, the safety and clinical efficacy of bertilimumab administered as 3 IV infusions over 4 weeks.

Secondary Objectives

• To evaluate the pharmacokinetics (PK) and pharmacodynamics (PD) of bertilimumab in patients with active moderate to severe UC.

2.2 STUDY ENDPOINTS AND OUTCOMES

2.2.1 Efficacy Endpoints

Primary

• Change in Mayo Score from screening to Day 56 (Visit 7). Clinical response at Day 56g will be defined as:

0	A decrease from the pre-treatment screening Mayo score of at least 3 points
	and at least 30%

AND

Protocol: Immune/BRT/UC-01 Page 20 of 58

^f In this protocol, "study drug" refers to either bertilimumab or placebo.

^g This and all other follow-up visits have a window of ± 3 days.

• Either a decrease from the pre-treatment screening sub-score for rectal bleeding of at least 1 point, or Rectal Bleeding Sub-score of 0 or 1.

Secondary

- Change in UCEIS score from screening to Day 56.
- Clinical remission at Day 56, defined as a total Mayo score of 2 points or lower, with no individual sub-score exceeding 1 point.
- Mucosal healing at Day 56, defined as an absolute sub-score for endoscopy of 0 or 1.
- Change in partial Mayo score from Day 0 to all scheduled measurement timepoints (efficacy follow up).

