- 20. Clinically significant abnormal laboratory test results, unless regarded by the Investigator as related to UC, including but not limited to:
 - Hemoglobin level <10.0 g/dL.
 - White blood cell count $< 3 \times 10^3/\mu L$.
 - Lymphocyte count $< 0.5 \times 10^3/\mu L$.
 - Platelet count $<100 \times 10^3/\mu L$ or $>1200 \times 10^3/\mu L$.
 - Alanine aminotransferase (ALT) or aspartate aminotransferase (AST)
 >3 × the upper limit of normal (ULN).
 - Alkaline phosphatase > 3 \times ULN.
 - Serum creatinine >2 \times ULN.
- 21. Active abuse of alcohol or drugs.
- 22. Known malignancy or history of malignancy that could reduce life expectancy.
- 23. Any condition, which in the opinion of the Investigator, would place the subject at an unacceptable risk if participating in the study protocol.
- 24. Participation in a clinical trial of an investigational (unapproved) product within 1 month of the screening visit.

Investigational Product, Route and Dosage Form	Bertilimumab is a recombinant human IgG ₄ monoclonal antibody that neutralizes human eotaxin-1 (eotaxin). The drug product consists of bertilimumab formulated in phosphate buffered saline (PBS) at a concentration of 10 mg/mL, presented as a sterile, clear, colorless solution in 10 mL clear glass vials. Polysorbate 20, a non-ionic surfactant to prevent protein aggregation, is added to the study drug vial during manufacture or to the saline infusion bag prior to subject dosing.
	Bertilimumab 10 mg/kg will be administered by IV infusion over 30 minutes.
Reference Therapy	A matching phosphate buffered saline (PBS) placebo containing polysorbate 20 will be administered by IV infusion over 30 minutes.
Prophylaxis for Prevention of Infusion Reactions	Subjects will be administered a pre-treatment regimen consisting of dexamethasone 10 mg PO 18-24 hours prior to administration of study drug (i.e., bertilimumab or placebo). One hour prior to administration of study drug, subjects will receive acetaminophen 1000 mg PO and either loratadine 10 mg PO or cetirizine 10 mg PO. In the event that dexamethasone was not administered previously, then 10 mg dexamethasone IV may be administered one to three hours prior to study drug administration.
Outcome	EFFICACY ENDPOINTS
Measures	Primary Endpoint
	• Change in Mayo Score from screening to Day 56 (Visit 7), where clinical response at Day 56° is defined as:
	 A decrease from the pre-treatment screening Mayo score of at least 3 points and at least 30%
	AND

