8.3 STATISTICAL METHODS

All measured variables and derived parameters will be listed individually. Outcomes will be summarized by treatment group, depending on their nature, as follows:

- For dichotomous variables: Categorization into success/failure-like categories; then incidence of failure and relative risk of failure in the active group compared to placebo with 95% confidence interval.
- For numeric continuous endpoints: Descriptive statistics and summary tables will include sample size, arithmetic mean, standard deviation, median, minimum and maximum, and 95% Confidence Interval (CI) for mean at the relevant time points by treatment.
- For ordered categories endpoints: incidences in the different categories and, after dichotomization into success/failure-like categories, incidence of failure and relative risk of failure by treatment with 95% confidence intervals.

All tests applied will be two-tailed, and p value of 0.1 or less will be considered statistically significant. Since this is an exploratory trial, there will be no Alpha-correction for multiple testing. The data will be analyzed using the SAS® 9.1 software package or higher (SAS Institute, Cary, North Carolina).

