8.3.4.1 Primary Endpoint Analysis

This study's primary endpoint analyses will be descriptive, providing proportion of Mayo Score Clinical Response separately by treatment group, including two-sided 95% Exact

Protocol: Immune/BRT/UC-01 Page 40 of 58 Final Version 8.0 May 23, 2018

^o a) The continuous UCEIS will be imputed using MI, after which clinical response will be computed and b) Should there be variables causing the MI model not to converge, these will be excluded from the model.

Binomial confidence intervals. Exploratory statistical testing will be done by comparing Bertilimumab treatment arm to placebo.

8.3.4.2 Secondary Endpoint Analyses

- a. Primary endpoint analysis described in the preceding section will be repeated in PP.
- b. Secondary endpoints will be analysed in both mITT and PP analysis sets.

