## 7.3 Secondary Efficacy Endpoints

- Change in Mayo Score from screening to Day 56 (Visit 7), calculated as
  - Change in Mayo Score = Mayo Score at Screening Mayo Score at Day 56
- Change in UCEIS score from screening to Day 56 (Visit 7), calculated as
  - Change in UCEIS score = UCEIS score at Screening UCEIS score at Day 56
- Clinical remission at Day 56 will be defined as
  - Success "1", if total Mayo score of 2 points or lower, with no relevant individual sub-score exceeding 1 point.
  - o Failure "0", otherwise.
- Mucosal healing at Day 56 will be defined as
  - O Success "1", if absolute sub-score for endoscopy of 0 or 1.
  - o Failure "0", otherwise.
- Change in partial Mayo score from Day 0 to all scheduled measurement timepoints (efficacy follow up) calculated as
  - Change in partial Mayo score = Partial Mayo score at Screening –
    partial Mayo score at Visit t

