## 9.4 Efficacy

#### 9.4.1 Primary Efficacy Analysis

Primary efficacy analysis will be conducted on mITT population. Because this is an exploratory study, alpha will be set at 0.1 for comparisons between groups.

- For each of the treatment groups, the incidence of success/ failure will be calculated along with a 90% exact binomial confidence interval.
- Additionally, descriptive statistics of total Mayo Score Clinical Response (Stool Frequency, Rectal Bleeding, Endoscopic Finding, Physician's Global Assessment and total score) will be presented by visit and treatment group including two-sided 95% Exact Binomial confidence intervals.

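### Change in total Mayo score is labelled primary in the protocol and secondary in the SAP, has no results line in SAP 9.4.2, and SAP 9.4.1 attaches exact binomial intervals to Mayo scores

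*Protocol*

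**What the plan says.** **Protocol, endpoint lists.** Section 2.2.1 names the primary endpoint as "Change in Mayo Score from screening to Day 56 (Visit 7") and follows it with the definition of clinical response. The synopsis joins the two in one sentence: "Change in Mayo Score from screening to Day 56 (Visit 7), where clinical response at Day 56" is then defined. The label is the numeric change; the definition is binary.

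**Protocol, analysis.** Section 8.3.4.1 deals only with response: "This study's primary endpoint analyses will be descriptive, providing proportion of Mayo Score Clinical Response separately by treatment group, including two-sided 95% Exact" binomial intervals. It names no analysis of the numeric change. Section 8.3 has a general rule for continuous endpoints: "For numeric continuous endpoints: Descriptive statistics and summary tables will include sample size, arithmetic mean, standard deviation, median, minimum and maximum", together with a "95% Confidence Interval (CI) for mean at the relevant time points by treatment". The synopsis version of that rule also asks for placebo-corrected results in the active arm.

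**SAP, endpoints.** Section 7.2 has clinical response as the only primary efficacy endpoint. The first item in 7.3, the secondary list, is "Change in Mayo Score from screening to Day 56 (Visit 7), calculated as" screening score minus Day 56 score.

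**SAP, analysis.** Section 9.4.1 gives the incidence of success and failure by arm with a 90% exact binomial interval. Its second bullet asks for descriptive statistics, by visit and arm, of stool frequency, rectal bleeding, endoscopy, physician's global assessment and the total score, "including two-sided 95% Exact Binomial confidence intervals". Section 9.4.2 has lines for change in UCEIS, remission, mucosal healing and change in partial Mayo. It has none for change in total Mayo.

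**The concern.** There are three linked faults.

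1. The two documents do not agree on which Mayo quantity is primary, and the protocol's endpoint label does not match its own analysis section.
2. The quantity that the protocol labels primary is the only SAP 7.3 endpoint without a planned results line.
3. The one SAP results bullet on the full Mayo scores asks for an interval that does not fit a score. A programmer would have to guess whether a proportion or a mean is meant.

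Protocol 8.2 says that the sample size was chosen to give reasonable precision in a first estimate of clinical effect. With at most 42 subjects, a difference in mean change with its interval is a natural part of that estimate. As written, the SAP does not deliver one.

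**Working it through.** The plan states no figure on this point. Protocol 8.2 gives up to 42 subjects with no response rate, SD, effect or power, so there is nothing to reproduce. The check is a comparison of texts plus two short calculations.

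**Step 1. SAP 7.3 endpoints against SAP 9.4.2.**

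| SAP 7.3 endpoint | Results line in 9.4.2 |
|---|---|
| Change in total Mayo | none |
| Change in UCEIS | yes |
| Clinical remission | yes |
| Mucosal healing | yes |
| Change in partial Mayo | yes |

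SAP 9.4.5 does not fill the gap: it presents primary endpoints by covariate level, and change is not primary in the SAP.

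**Step 2. What the SAP does yield for the total score.** The second bullet of 9.4.1, with the general numeric format in section 9 (mean, SD, minimum, median, maximum, n; no interval), gives the total score at each visit by arm. Full Mayo is scheduled only at screening, Visit 7 and early discontinuation. In subjects with both scores, mean change is the difference of the two visit means. Its SD is not recoverable from those tables: SD(change)² = s₁² + s₂² − 2·r·s₁·s₂, and the within-subject correlation r is not reported. Without that SD there is no interval for the change and none for a difference between arms.

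**Step 3. Whether an exact binomial interval fits.** The Clopper–Pearson interval takes a count x with 0 ≤ x ≤ n. Its limits are the α/2 quantile of Beta(x, n − x + 1) and the 1 − α/2 quantile of Beta(x + 1, n − x).

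- For response it works. At illustrative counts, 14/28 gives a 95% interval of 30.6% to 69.4%, and 4/14 gives 8.4% to 58.1%.
- For a mean score it does not. SAP section 8 defines sub-scores of 0–3 and a total of 0–12. Fourteen subjects averaging 8 points sum to 14 × 8 = 112, which exceeds n = 14. Counting 112 out of 14 × 12 = 168 possible points would not rescue it, because points within a subject are not independent trials.

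**Step 4. Precision that a change analysis would have (illustrative).** Inputs: 28 versus 14, from 2:1 allocation of 42 (protocol sections 3 and 8.2); SD of change 2.0 to 3.5 points, **assumed**, because the documents give none.

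- Mean change by arm, 95% half-width = t × SD/√n. Active: 2.052 × SD/√28 = 0.78 to 1.36. Placebo: 2.160 × SD/√14 = 1.15 to 2.02.
- Unadjusted difference between arms: √(1/28 + 1/14) = 0.327. The 95% half-width is 2.021 × 0.327 × SD = 1.32 to 2.32 points. The 90% half-width is 1.684 × 0.327 × SD = 1.10 to 1.93 points.

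The textual faults in steps 1 to 3 do not depend on the assumed SD.

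**The case against.** **A reader might infer that the SAP demoted the protocol's primary endpoint.** The documents do not support that. Protocol 8.3.4.1 already analyses only the response proportion as the primary endpoint. The footnote to the imputation rules in protocol 8.3.1.2 has the continuous score imputed first and response computed from it. The SAP follows the protocol's analysis section, and the mismatch begins inside the protocol. What stands is that the labels in the synopsis and 2.2.1 still need to be aligned.

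**A reader might infer that change in Mayo gets no summary at all.** That is too strong. Total scores by visit and arm are planned, mean change in subjects with both scores follows from them, and protocol 8.3 calls for a confidence interval for the mean of any continuous endpoint. What stands is that the SAP, which should turn the general rule into an output, has no line for it, and its own numeric format omits the interval.

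**A reader might infer that the interval in SAP 9.4.1 can never be computed.** That bullet opens by referring to Mayo clinical response, and protocol 8.3 allows ordered categories to be reported as incidences or dichotomised. Exact binomial intervals are valid for those. They are invalid if read as intervals for mean scores, and the bullet's own list of sub-scores and total invites that reading.

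**The missing between-arm contrast is not peculiar to this endpoint.** SAP 9.4.2 also leaves change in UCEIS and partial Mayo as descriptive statistics by arm, which fits the exploratory design. That is fair. Adding a contrast for total Mayo is a recommendation; the missing line is the documented gap.

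**A reader might quantify the information lost by dichotomising with a normal model and a single 3-point cut.** The documents do not support such a figure. They give no SD, and the response rule is not a single cut: a 30% fall means 4 points from a screening score of 11 or 12 (3.3 and 3.6 rounded up), and a rectal-bleeding condition applies as well.

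**Conclusion.** The point holds as a specification fault that should be corrected. The primary label is inconsistent between the protocol's endpoint lists and both documents' analysis sections. Change in total Mayo is the one SAP 7.3 endpoint of five with no results line in 9.4.2. The second bullet of SAP 9.4.1 attaches an interval for proportions to scores.

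The consequence is limited. The trial is exploratory and descriptive, so no type I error claim depends on this, and the response analysis itself is soundly specified. What would be missing is the SD and interval for the change and any between-arm estimate of it. If the SD of change lies between 2.0 and 3.5 points, an assumption without support in the documents, 28 versus 14 subjects would give a 95% half-width of about 1.3 to 2.3 Mayo points for that difference. Fewer subjects or incomplete Visit 7 data would widen it.

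**What to change.** 1. Name clinical response at Day 56 as the primary endpoint in the protocol synopsis and section 2.2.1, matching protocol 8.3.4.1 and SAP 7.2. List change in total Mayo as secondary in both documents.
2. Add a line to SAP 9.4.2 for change in total Mayo from screening to Day 56, in mITT and PP: n, mean, SD, median and range by arm with a t-based or bootstrap interval for the mean, and a between-arm difference from a linear model with treatment, screening Mayo and prior anti-TNF stratum. Report the difference with 90% and 95% intervals, labelled exploratory.
3. Reword the second bullet of SAP 9.4.1. Keep exact binomial intervals for response, remission and mucosal healing, and give score means an interval for a mean, as protocol 8.3 requires.

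Cost: SAP wording, a protocol label clarification and one extra model. No new data are needed, since screening Mayo and the stratum are already collected.
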